3.2 Secondary Objectives

To establish corticospinal tract lesion load as a correlate of kinematic and neuromuscular responsiveness to exoskeletal support. We do this by associating the change in RC (or MC) with the variance in overlap between the lesion and the corticospinal tract (CST lesion load) using clinical standard of care MRI scans.

4 Study Design and Endpoints

4.1 Description of Study Design

In this study, we aim to use a virtual reality reaching task with exoskeletons to increase use of the impaired limb in stroke survivors. For all participants, they will complete 3 blocks of 54 trials in a single session. Block 1 is a baseline phase where subjects will perform reaches without any loads applied via the exoskeleton devices. Block 2 is the intervention block where bilateral exoskeletons apply gravity assistance to the impaired arm for stroke survivors and gravity resistance to the non-impaired arm. In healthy controls, assistance is applied to the non-dominant arm and resistance is applied to the dominant arm. Block 3 is a retention block, where tested procedures are identical to block 1.

Virtual Reality Task

In each block, the subject will be asked to sit on a chair, wear the Oculus headset, and hold a touch controller in each hand to reach through a target displayed in the VR system (Figure 1). Subjects can see two avatar's hands, representing their own hands movements, in the VR environment. Each experimental block includes 54 trials. In each trial, the subject is asked to put his/her hands on his/her laps as a starting position. After the start position is achieved, a target cube will show up in the VR environment and the subject will use both hands to reach the cube. A cursor, located at the midpoint of the hands, will be used to 'hit' the target cube during each trial. The same horizontal locations of the targets used in a previous VR study will be used (Wang et al., 2021). Target locations will span the workspace from approximately ± 15 degrees located at shoulder and eye level. This distribution is chosen to simulate reaches typically made in activities of daily living. The sequence of target locations will be randomized. Subjects' hand movements will be confined to a quadrant and the radius will be scaled to each subject's arm length, within the subject's comfortable range of motion. Subjects can move at their own comfortable speed.

Figure 1: Oculus Rift headset and touch controller bundle

Exoskeleton device

Subjects will be asked to wear an exoskeleton device (Figure 2). This exoskeleton was designed and constructed by our lab to provide either gravity assistance or gravity resistance. Gravity assistance will be applied to the impaired arm of stroke patients and to the non-dominant arm of healthy controls. Gravity resistance will be applied to the non-impaired arm of stroke patients and to the dominant arm of healthy controls. Assistance/resistance levels are adjusted to provide a 50% change in arm weight based on the shoulder torque required to abduct the upper extremity. For example, for a 150lb person, the 50% resistance configuration would simulate adding a weight, W, equal to 2.33 lbs. at the wrist ($0.5*T = 0.5*BW*0.0533*0.447 = W*0.7687$) (Plagenhoef et al., 1983). More detail on the exoskeleton device is in Section 6 Study Agent.

Electromyography

Muscle activity will be measured using surface electromyography (EMG). Non-invasive electrodes (Biometrics Ltd, UK) will be applied to the skin of the subject over several muscles of interest including anterior deltoid (bilaterally), triceps (bilaterally) and the short head of the biceps brachii (bilaterally). Maximum voluntary contraction will be assessed 3 times for both forward shoulder abduction and elbow flexion. Participants will be asked to produce a maximum force for 3-5 seconds while experimenters measure muscle activity. Sixty seconds of rest will be provided between MVC assessments. These data will be used to normalize outcome measures. EMG muscle activity will be recorded throughout each session.

Figure 2: Exoskeleton in gravity resistance configuration

Neuroimaging

Finally, we will obtain neuroimaging data from the participant's electronic medical record (EMR). The Study Investigator will obtain written consent (see Consent Form) to access the participant's EMR, where they will download the diffusion weighted image (DWI) scan obtained through standard of care at NYULMC. **No new imaging will be required.** Downloaded DWI images will have personal identifying information removed. The DWI will be analyzed in the ITK-SNAP (<http://www.itksnap.org/pmwiki/pmwiki.php>). We use this software to manually trace the lesion to obtain a lesion mask. This lesion mask is then standardized to the Montreal Neurological Institute stereotaxic space (Mazziotta et al., 2001) using the SPM12 mapping software (Karl Friston, <https://www.fil.ion.ucl.ac.uk/spm/>). We then determine the overlap between the lesion mask and the CST (Zhu et al., 2010).

Study Timeline

The study will take place on the NYULMC campus in a single, 2-hour session.

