5.1 Inclusion Criteria

In order to be eligible to participate in this study, an individual must meet all of the following criteria:

Healthy controls

1. Having obtained the age of 18 years
2. Neurologically healthy (i.e., no history of: traumatic brain injury, peripheral neuropathy, seizures, etc.)
3. Strongly right-handed according to at least 80% score on the Edinburgh Handedness Inventory (Oldfield, 1971; Veale, 2013). The use of right-handed participants is a common feature in this field of study. This is due to the slight differences in arm control between left- and right-handed individuals (Sainburg & Kalakanis, 2000).
4. Ability to give informed consent

Survivors of stroke

1. Having obtained the age of 18 years
2. have a diagnosis of stroke more than six months prior to entry into the study;
3. have the ability to reach, unsupported, to approximately 70% of arm length
4. ability to give informed consent

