10.4 Description of Statistical Methods

10.4.1 General Approach

This study is a repeated measures cohort design. Two groups of participants (stroke, healthy control) will perform a reaching task with and without an exoskeleton device. Primary endpoint measures will be compared within-subject to assess the effects of exoskeleton loading on coordination (kinematic: RC and muscular: MC). A between-subjects analysis will be performed to assess differences in arm control between stroke and healthy control participants.

- For descriptive statistics, we will use ranges, means, and standard deviation as appropriate. For example individual ages will be reported and further summarized with mean and standard deviation.
- For inferential statistics, we will perform two-tailed paired- and unpaired t-tests and ANOVA where appropriate. Statistical significance will be assessed at the Type-I error less than $p = 0.05$ level. See Section 10.4.2.
- Covariates will not be pre-specified
- Statistical test assumptions will be analyzed following data collection. Appropriate adjustments (e.g., normality) will be performed, such as transformation or the use of non-parametric tests.

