10.4.2 Analysis of the Primary Efficacy Endpoint(s)

Primary study objective (change in RC, MC)

- Two-way ANOVAs on RC are conducted with within-subjects factor block (baseline, loading, retention) and between-subjects factor cohort (healthy, stroke). Three-way ANOVAs on MC are performed with within-subjects factors block and muscle (deltoid, biceps) and between-subjects factor cohort.

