10.6 Measures to Minimize Bias

10.6.1 Enrollment/Randomization/Masking Procedures

Enrollment will be initiated by the study investigator, [name]. [name] will contact participants via phone, SendSafe Secure email, or MyChart. Stroke participants will be contacted if they meet the inclusion criteria and assigned to the stroke group. Healthy control participants will be recruited on a rolling basis to match the age and gender of the stroke group. There is no randomization, blinding, or masking proposed.

11 Source Documents and Access to Source Data/Documents

Source data is all information, original records of clinical findings, observations, or other activities in a clinical trial necessary for the reconstruction and evaluation of the trial. Source data are contained in source documents.

Examples of these original documents, and data records include: hospital records, clinical and office charts, laboratory notes, memoranda, subjects' diaries or evaluation checklists, pharmacy dispensing records, recorded data from automated instruments, copies or transcriptions certified after verification as being accurate and complete, microfiches, photographic negatives, microfilm or magnetic media, x-rays, subject files, and records kept at the pharmacy, at the laboratories, and at medico-technical departments involved in the clinical trial. It is acceptable to use CRFs as source documents. If this is the case, it should be stated in this section what data will be collected on CRFs and what data will be collected from other sources.

The study case report form (CRF) is the primary data collection instrument for the study. All data requested on the CRF must be recorded. All missing data must be explained. If a space on the CRF is left blank because the procedure was not done or the question was not asked, write "N/D". If the item is not applicable to the individual case, write "N/A". All entries should be printed legibly in black ink. If any entry error has been made, to correct such an error, draw a single straight line through the incorrect entry and enter the correct data above it. All such changes must be initialed and dated. DO NOT ERASE OR WHITE OUT ERRORS. For clarification of illegible or uncertain entries, print the clarification above the item, then initial and date it.

12 Quality Assurance and Quality Control

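### The reference arm is always non-dominant in controls but of either dominance in the stroke group, so the baseline and overall stroke-control comparisons, chiefly of RC, mix stroke with arm dominance

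*Combined protocol and SAP*

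**What the plan says.** Section 4.1 sets the loading rule for controls: "In healthy controls, assistance is applied to the non-dominant arm and resistance is applied to the dominant arm". It then gives the rule for both cohorts: "Gravity assistance will be applied to the impaired arm of stroke patients and to the non-dominant arm of healthy controls". Resistance goes to the opposite arm, and section 6.1 repeats the scheme.

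Section 5.1 requires controls to be "Strongly right-handed according to at least 80% score on the Edinburgh Handedness Inventory", so their assisted arm is always the left. It explains the restriction: "This is due to the slight differences in arm control between left- and right-handed individuals". The four stroke criteria cover age, time since stroke, consent and reach ("have the ability to reach, unsupported, to approximately 70% of arm length"). None concerns handedness or affected side. Section 7.1.2 says handedness data serve eligibility screening, but 5.1 sets a threshold for controls only.

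On matching, 10.6.1 says: "Healthy control participants will be recruited on a rolling basis to match the age and gender of the stroke group". Section 10.4.6 describes equal numbers of men and women and age matching across groups. On adjustment, 10.4.1 says: "Covariates will not be pre-specified".

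The cohorts are compared in the baseline t-tests on RC and MC (10.2) and in the ANOVAs with cohort as between-subjects factor (10.4.2). Neither has a term for dominance or side. Handedness (10.3, 14.1) and left or right stroke location (14.1) are collected, but no planned analysis uses them.

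**The concern.** Section 3.1 describes the kinematic question as displacement of the impaired arm relative to the other arm. If RC measures this, its value depends on which arm is the reference. The protocol treats handedness as important enough to restrict controls, yet leaves it free in the stroke group. The share of participants whose reference arm is dominant is then zero in one cohort by design and uncontrolled in the other.

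At stake is the reading of a cohort difference. Section 3.1 places the comparison with controls within both primary objectives, and 10.2 adds baseline cohort contrasts as a secondary endpoint. A difference in level could reflect stroke, dominance or both, and the planned analysis cannot tell which.

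**Working it through.** **1. The plan's own figure.** Section 10.5 gives a total of 20-28 for Cohen's f = 0.25-0.3, power 0.8 and significance level 0.05. This reproduces as the block-by-cohort interaction with 3 blocks and 2 groups, assuming correlation 0.5 between blocks and sphericity (neither is stated). With λ = f² × N × 3 / (1 − 0.5):

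- f = 0.25, N = 28: λ = 0.0625 × 28 × 3 / 0.5 = 10.5; df 2 and 52; power 0.812.
- f = 0.30, N = 20: λ = 0.09 × 20 × 3 / 0.5 = 10.8; df 2 and 36; power 0.812.

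Sizing for the cohort main effect would have needed 86 and 62. The study thus appears to be sized for a stroke-control comparison, though for the interaction rather than the difference in level.

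**2. Will the stroke group contain dominant-impaired participants?** Let q be the share with the dominant arm impaired (not given; assumed). The chance of at least one among 12 is 1 − (1 − q)^12: 93.1% at q = 0.2, 98.6% at q = 0.3 and over 99.9% at q = 0.5. In controls the share is 0.

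**3. Bias in a difference in level.** Let g be the shift in the outcome, in SD units, when the reference arm is dominant (not given; assumed). Stroke mean minus control mean has expectation (stroke effect) + q × g − 0 × g, so the bias is q × g.

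**4. Effect on the baseline t-test.** Simulation: 12 v 12, normal outcomes, no stroke effect, two-sided 5% unpaired t-test, 20,000 runs per cell. Each cell shows bias in SD, then type I error.

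| q | g = 0.25 | g = 0.5 | g = 1.0 |
|---|---|---|---|
| 0.3 | 0.075; 5.3% | 0.15; 6.2% | 0.30; 10.4% |
| 0.5 | 0.125; 5.8% | 0.25; 8.9% | 0.50; 20.1% |
| 0.7 | 0.175; 6.9% | 0.35; 12.7% | 0.70; 34.4% |

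When each simulated control was given the same reference-arm dominance as a stroke participant, the expected bias was 0 and the error rate 3.1-4.9%. It falls below 5% because the unpaired test ignores the matching.

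**5. Bias in responsiveness.** Let the shift be g(base) at baseline and g(load) under loading. The bias in the cohort difference in change is q × (g(load) − g(base)). A constant shift gives exactly 0, so the table does not apply to the block-by-cohort term.

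**6. Analyses without controls.** The paired t-tests of RC and MC within stroke participants (10.2), which address the 2% and 5% endpoints of 4.2.1, and the lesion-load regressions (10.4.3) contain no control data. Their bias from this source is 0.

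**7. Precision of a restricted analysis.** At 12 v 12, 80% power needs a difference d of about 1.20 SD. If half the stroke group is dominant-impaired, restriction leaves 6 v 12. The noncentrality is then 1.20 × √(6 × 12 / 18) = 1.20 × 2 = 2.40 on 16 df, giving power of about 62%.

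**The case against.** The strongest reply is that the two primary hypotheses compare stroke participants with themselves, so the mixing touches neither. That stands. A reader might infer that the bias can be set against the 2% RC endpoint. It cannot, because that threshold concerns a within-stroke change and the bias is a between-group difference.

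A reader might also infer that every stroke-control comparison is compromised. The documents do not support that. A constant dominance shift cancels out of the responsiveness term, and nothing in the protocol shows that dominance alters the response to loading. RC and MC are not defined in the visible text, so the dependence of RC on the reference arm is inferred from 3.1. The same section speaks of bilateral muscle activity, and the MC ANOVA has no arm factor. If MC pools both arms, its baseline comparison would be less affected.

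Next, the protocol calls the differences in arm control slight, which favours the left-hand columns of the table over the right. Direction is also open. Section 10.2 expects lower RC in stroke; if a dominant reference arm raises RC, the mixing would hide that difference rather than create it.

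Finally, 10.4.6 and 10.6.1 describe matching of groups, not individual pairs, so a remedy built on pairs does not fit the plan. This also stands.

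What none of this removes is the asymmetry itself. No criterion, matching variable or model term addresses it.

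**Conclusion.** The concern holds for comparisons of level between cohorts: the baseline t-tests and the cohort main effect, chiefly for RC. It holds for the block-by-cohort term only if dominance modifies the response to loading, and probably less for MC if that measure pools both arms.

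The size is unknown. Under assumed q = 0.3-0.7 and g = 0.25-0.5 SD, the bias is 0.075-0.35 SD and the nominal 5% t-test rejects about 5-13% of the time without a stroke effect. The roughly 20% at q = 0.5 and g = 1 SD needs an effect that sits poorly with the protocol's own description. The mixing would vanish if every enrolled stroke participant had the non-dominant arm impaired, which the plan does not require. It deserves correction because it bears on objectives stated in 3.1 and the remedy is cheap, but it does not threaten the within-stroke results.

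**What to change.** **Preferred.** Add reference-arm dominance to the group-level matching in 10.4.6 and 10.6.1. Controls are recruited on a rolling basis, so the share of controls analysed with the dominant arm as reference can be set equal to the share in the stroke group. How the arms are loaded stays with the investigators. For the unloaded baseline block, the reference arm is only a label in the analysis.

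**At minimum.** Derive a variable for whether the impaired arm is dominant (yes/no) from the handedness and stroke-side data already collected, and report its distribution. Pre-state a sensitivity analysis of the cohort comparisons restricted to stroke participants whose non-dominant arm is impaired, and qualify the cohort conclusions if it differs from the main result. Under the current set-up the variable is always no in controls. Entering it as a model factor would therefore also estimate the cohort contrast from those participants only.

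**Also.** Define RC and MC, and say whether MC pools both arms, so that the exposure of each comparison is clear.

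**Cost.** A sentence on matching, one derived variable and one pre-stated analysis, with no new visits or measurements. The matched set-up would depart from the earlier healthy-control study. Left-handed stroke participants would still be compared with right-handed controls. The sensitivity analysis is imprecise: with about 6 v 12, power falls from 80% to about 62% for the same difference, so failure to confirm the main result would not refute it.

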2.4 Potential Risks & Benefits

2.4.1 Known Potential Risks

Potential risks of the exoskeleton include arm fatigue and soft-tissue (e.g., muscle, skin) discomfort. Fatigue is not greater than minimal risk because the arm movements will mimic reaching for an object on a shelf at eye level. No more than 54 reaches will be made in any single testing block, and these reaches are self-paced. Soft-tissue discomfort may arise from the exoskeleton applying a force to the arm. Discomfort poses no greater than minimal risk because the participant will only wear the device for approximately 5 minutes during the data collection phase. Also, the magnitude of force applied to the arm is no more than 50% of that due to gravity. The upper arm weighs approximately 5.77% of body weight ((Plagenhoef et al., 1983). For example, a 150 lbs. person would receiving a loading amount to counter 8.65 lbs. of force. The exoskeleton device will be worn during all testing blocks, however, the load is only applied during the 'loading phase' which lasts approximately 5 minutes.

It is anticipated that participants may be inconvenienced by the amount of time necessary to complete the study and may experience fatigue because of completing required reaching tasks in the VR system. Very rarely, participants may experience short-term dizziness or headache because of using the head mounted display of the VR system. Participants will be given ample time for practice and rest, and they may take a break and/or discontinue the study at any time.

To limit the risks associated with VR headset and exoskeleton use, we will provide the participant with breaks every 5-minutes. Also, all reaches will be self-paced. Participants will be verbally instructed that they may request unscheduled breaks during the data collection blocks. These unscheduled breaks will not affect data integrity. We also use padding and elastic gauze on the arms to reduce pressure and abrasion risk.

There is a potential risk of breach of confidentiality. To mitigate this, procedures will be carried out in a laboratory space on the NYULMC campus. We are requesting personal health information from the patient's medical record. To mitigate this, access will only be granted to named persons on this protocol; data will be stored on TrialMaster.

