10.2 Statistical Hypotheses

Primary endpoint. Exoskeletal support will increase RC in stroke participants. Paired t-test comparing RC from baseline to loading blocks.

Primary endpoint. Exoskeletal support will decrease MC in stroke participants. Paired t-test comparing MC from baseline to loading blocks.

Secondary endpoint. There will be an association between change in RC (or MC) and CST lesion load. Independent linear regressions (RC vs. CSTLL and MC vs. CSTLL).

Secondary endpoint. RC values in stroke participants will be less than RC values in healthy controls during baseline blocks (t-test). MC values in stroke participants will be greater than MC values in healthy controls during baseline blocks (t-test).

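### Loading always comes second, so the paired baseline-to-loading tests of RC and MC cannot separate an exoskeleton effect from practice or fatigue drift; a block 3 sensitivity contrast would partly address this

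*Combined protocol and SAP*

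**What the plan says.** Every participant completes three blocks of 54 reaches in one session, always in the same order (section 4.1):

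- First: "Block 1 is a baseline phase where subjects will perform reaches without any loads applied via the exoskeleton devices".
- Second: "Block 2 is the intervention block where bilateral exoskeletons apply gravity assistance to the impaired arm for stroke survivors", with resistance on the other arm.
- Third: "Block 3 is a retention block, where tested procedures are identical to block 1".

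Within a block the target sequence is randomized, but the block order is not. Section 10.6.1 states: "There is no randomization, blinding, or masking proposed".

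Both primary hypotheses in section 10.2 concern stroke participants and use the first two blocks. For RC the test is "Paired t-test comparing RC from baseline to loading blocks" and for MC it is "Paired t-test comparing MC from baseline to loading blocks".

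Section 10.4.2, on the primary efficacy endpoints, plans ANOVAs. The one for RC has "within-subjects factor block (baseline, loading, retention) and between-subjects factor cohort (healthy, stroke"); the one for MC adds muscle as a factor. No contrast among the three blocks is named.

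Section 2.4.1 expects that participants "may experience fatigue because of completing required reaching tasks in the VR system". It also provides self-paced reaches and a break every 5 minutes. Section 7.2 adds VR practice before data collection, without saying how much.

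**The concern.** Section 3.1 asks a causal question: what gravity compensation does to coordination and muscle activity in stroke. The paired tests compare an earlier block with a later one, and loading is switched on between them. If RC or MC moves over 54 reaches for any other reason, such as learning the shared-cursor task or tiring, that movement is counted as effect of the device. Drift in the hypothesized direction produces false positives; drift against it hides a real effect.

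The ANOVA does not settle this as written. An overall block effect also responds to drift. The block-by-cohort term removes drift that stroke and control participants share, but it removes the shared loading effect too and leaves any stroke-specific fatigue in place. It therefore answers a different question from the within-stroke hypothesis.

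The same change scores enter the lesion-load regressions (sections 10.4.3 and 10.5). Drift common to everyone would shift only the intercept there; drift that differs between participants would add error.

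**Working it through.** **Inputs from the documents.** Fixed three-block order (4.1); paired two-tailed tests of block 2 against block 1 (10.2, 10.4.1); alpha 0.05 (10.4.1); 12 stroke participants (Protocol Summary, 10.5). No SD, within-person correlation or drift figure is given. Drift is therefore an assumed range, in units of the SD of the paired difference.

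**1. The plan's own figure.** Section 10.5 gives a total of 20-28 for f = 0.25-0.30, power 0.8 and alpha 0.05. For a repeated-measures ANOVA with 2 groups and m measurements, the noncentrality is λ = f²·N·m/(1 − ρ). Assume ρ = 0.5 and sphericity, neither of which is stated.

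- m = 3, f = 0.25, N = 28: λ = 0.0625 × 28 × 3 / 0.5 = 10.5, power 0.812.
- m = 3, f = 0.30, N = 20: λ = 0.09 × 20 × 3 / 0.5 = 10.8, power 0.812.
- m = 2 would need N = 34 and N = 24.

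Under these assumptions the stated range matches three blocks, not two. The sample size thus appears to rest on the ANOVA that includes block 3.

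**2. Drift in the planned paired test.** Let the true loading effect be L and let drift add d at block 2. Then block 2 − block 1 estimates L + d. With n = 12 the paired test has 80% power at a standardized difference of 0.889. From the noncentral t distribution:

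| Assumed drift (SD of paired difference) | Error rate when L = 0 | Power if drift opposes an effect of 0.889 |
|---|---|---|
| 0 | 5.0% | 80.0% |
| 0.1 | 6.2% | 70.1% |
| 0.2 | 9.7% | 58.5% |
| 0.3 | 15.8% | 46.1% |
| 0.5 | 35.3% | 23.4% |

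**3. The averaged contrast, block 2 − (block 1 + block 3)/2.**

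- Linear drift (0, d, 2d): d − (0 + 2d)/2 = 0. Simulated error rate 0.051 at drifts of both 0.3 and 0.5.
- Drift that levels off (0, d, d): d − d/2 = d/2. Half remains, and the error rate is 8.5% at drift 0.3 and 15.0% at 0.5.
- Precision under equal correlation: the variance is 1.5σ²(1 − ρ), against 2σ²(1 − ρ) for block 2 − block 1. The SE ratio is √0.75 = 0.866.
- Carry-over of a fraction c of L into block 3: L − cL/2 = L(1 − c/2).

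For the effect that gives the planned test 80% power, and with no drift, the averaged contrast has power 0.898 at c = 0, 0.829 at c = 0.2, 0.680 at c = 0.5 and 0.368 at c = 1. It matches the planned test where 1 − c/2 = 0.866, that is c = 0.268.

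**4. How the two contrasts relate.** Block 2 − (block 1 + block 3)/2 = (block 2 − block 1) − (block 3 − block 1)/2. They differ by exactly half of block 3 − block 1. Under linear drift with carry-over, block 3 − block 1 estimates 2d + cL. It shows how far the two readings diverge, but not whether drift or carry-over is the reason.

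**The case against.** Four points can be made for the plan as it stands.

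- **Block 3 is already in the primary analysis section.** This is correct. A reader might infer from section 10.2 alone that the retention block is ignored, but section 10.4.2 includes it and the sample size appears to be built on it. The gap is narrower: no contrast is named that uses it against drift.
- **Breaks, self-pacing and practice limit drift.** They probably do, and the fatigue sentence in section 2.4.1 is a risk statement, not evidence that RC or MC moves. RC compares one arm with the other, so drift common to both arms should partly cancel. None of this measures what remains. MVC, taken once after the task (section 7.2), scales all blocks alike and cannot correct change between blocks.
- **Block 3 exists to measure retention.** This is the strongest point. A reader might infer that the third block could remove drift at no cost. It cannot: the contrast assumes linear drift and no carry-over, and three blocks in one order cannot tell non-linear drift from carry-over. For the same reason, requiring both contrasts to agree before crediting the device would be a poor rule, because it could reject a real effect that persists.
- **This is a small pilot without a formal SAP.** That is a reason to leave the primary test alone and ask only for a sensitivity analysis, which is what is proposed.

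**Conclusion.** The concern holds in a limited form. With loading always second and no randomization of order, the stroke-only paired tests of RC and MC cannot distinguish an exoskeleton effect from practice or fatigue drift, and no planned contrast does so.

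The size is unknown. The error rates of 6.2% to 35.3% follow from assumed drifts of 0.1 to 0.5 SD with n = 12; they show sensitivity and are not estimates for this study. A reader might infer that drift is present, or that it makes up some share of the 2% RC or 5% MC targets. The documents support neither, and they do not say whether those percentages are absolute or relative.

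The averaged contrast is a useful check, exact for linear drift and more precise than block 2 − block 1 under equal correlation. It is not a full remedy: half of a levelling-off drift remains, and carry-over shrinks the estimate to (1 − c/2) of the loading effect. This is a cheap improvement, not a flaw that invalidates the design.

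**What to change.** Keep the block order and the primary paired tests. Add to section 10.4.2, for RC and MC in stroke participants:

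1. A sensitivity contrast, block 2 − (block 1 + block 3)/2, with its 95% confidence interval.
2. Block 3 − block 1, with its 95% confidence interval, reported beside it.
3. A statement of the assumptions: the contrast removes drift only if it is linear across blocks (half remains if drift levels off after block 2), and it understates the loading effect by c/2 if a fraction c carries over into block 3.
4. A reading rule: if the contrasts disagree, report that the change cannot be attributed to loading alone from these data, rather than that there is no effect. A non-significant block 3 − block 1 with 12 participants should not be read as proof of no drift.

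The cost is one extra contrast per outcome, plus one reported difference, on data already collected. The downside is that the contrast is conservative under carry-over.
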